**Adjunctive Nitrous Oxide during ED propofol sedation in adults,
a pilot study.**

NCT02410707

Version: 7/1/14

Investigator(s): [name], DO; [name], DO; [name]; [name], CCRC

Objectives

To describe the safety and efficacy of adjunctive nitrous oxide pre-propofol administration for analgesia and pre-procedure anxiolysis during ED procedural sedation and analgesia in adults.

Background

Specific Aims

To measure the rates of hypoxia and respiratory depression requiring a physician intervention in adult patients receiving 50% demand valve nitrous oxide pre-propofol administration during ED procedural sedation and analgesia. Secondary aims include patient, nursing, and physician post procedure satisfaction scores, Ramsay sedation scores, total propofol dose given, length of time spent using nitrous oxide, patient recall of procedure.

Significance

Procedural sedation is the use of sedative, analgesic, and/or dissociative agents to relieve anxiety and pain associated with diagnostic and therapeutic procedures. Propofol has become one of the most commonly used agents for ED procedural sedation.^{1,2} Propofol crosses the blood-brain barrier rapidly. The drug takes effect within approximately 40 seconds, and its

duration of action is approximately six minutes^{2,3} Multiple randomized trials and prospective observational studies have found propofol to be safe and effective for PSA in the emergency department^{3,4,5}. Propofol acts as a sedative and amnestic, but provides no analgesia.

A possible approach is pretreatment with short-acting opioids (eg, fentanyl). Unfortunately, the addition of opioids increases the likelihood of respiratory complications. As an example, fentanyl at a dose of 1.5 mcg/kg increases the risk of respiratory depression. In another study, patients given both alfentanil and propofol required stimulation to induce respiration more often than those given only propofol.⁷ Another alternative to pretreatment with short-acting opioids is to use sub-dissociative doses of ketamine (0.3 mg/kg). Ketamine appears to provide comparable analgesia with less risk of respiratory depression. However, there is no literature that has shown that there is a decreased risk of respiratory depression than with propofol.⁸

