The optimal agent for analgesia before procedural sedation would have effect that is short acting, easy to administer, and with minimal risk to the patient. Nitrous oxide may fit this profile. In pediatric emergency departments, inhaled nitrous oxide was found to be the most common agent for procedural sedation and analgesia.⁸ There is a great deal of literature supporting the use of nitrous oxide in the pediatric population, and the safety and efficacy of its use as a single agent or in concert with a parenteral sedative and/or analgesic is excellent. However, there is a paucity of literature to support or refute the use of nitrous oxide in adults for ED procedural sedation and analgesia.

Nitrous oxide is a colorless gas that diffuses rapidly across the pulmonary alveoli providing analgesia and anxiolysis with minimal sedative effects, rapid induction, and emergence.⁹ Nitrous oxide is a weak sedative agent with the potential for significant analgesic

effects. Noncompetitive antagonist activity at the NMDA receptor along with activation of opioidergic receptors contributes to its anesthetic mechanism.¹⁰ In an RCT (ENIGMA 1) using anesthesia with and without nitrous oxide, there was a small increased risk of myocardial infarction in the nitrous oxide group.¹¹ However, there were patients getting general anesthesia for over two hours; our patients will be receiving 50/50 nitrous oxide for 5-10 minutes maximum, and there are no known cardiac side effects reported during short-term sedation in the literature.¹¹ There are rare adverse events, most often cited as case reports of chronic or acute toxicity causing myeloneuropathies and polyneuropathies.¹²⁻¹⁵

Nitrous oxide has been used in general anesthesia for over 2 centuries, but its use outside of the operating room began when Tunstall introduced the nitrous oxide/oxygen mixture as an analgesic agent during labor.¹⁶ Since this inception, the nitrous oxygen/oxygen mixture has been used readily in the fields of dentistry, gastrointestinal procedures, and children's procedural sedation. Nitrous oxide is often administered via continuous flow or on-demand at a concentration of 50-70%.

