Nitrous oxide has been shown to be a safe and effective agent for procedural sedation in children, including work that has combined opiates and benzodiazepines with nitrous oxide continuously. Burton et al. (1998) conducted a small, randomized controlled trial studying the effectiveness of nitrous oxide on anxiety scores in children during laceration repairs. They found a significant decrease in the group that used nitrous oxide compared to the placebo group.²⁰ This finding was further validated by Luhmann et al. (2001) with 50% continuous flow of nitrous oxide resulting in less distress and anxiety as well as increased patient satisfaction compared to midazolam or topical anesthetic agents²¹. The study also showed that the main adverse event associated with nitrous oxide was nausea and vomiting, whereas the midazolam group had significant ataxia and dizziness. There was no demonstrable advantage of the combination of midazolam and nitrous oxide in regard to patient satisfaction versus nitrous oxide alone, but there was an increase in adverse events when midazolam was included.²¹ A study performed by Evans et al. (1995) demonstrated that the pain and memory of the procedure between children receiving either nitrous oxide versus children receiving intramuscular meperidine in combination with promethazine for fracture reduction was similar, but there was increased satisfaction and decreased length of stay in the nitrous oxide group.²² Seith et al. (2012) demonstrated that the addition of intranasal fentanyl to nitrous oxide in children resulted in deeper levels of sedation when compared to nitrous oxide alone; however, there were no serious adverse events.²³

Nitrous oxide as an adjunct to propofol may be an ideal agent to decrease pre-procedure anxiety before deep sedation of adults in the ED. Nitrous oxide has some analgesic and anxiolytic qualities, with an excellent cardio-respiratory profile. The anxiety and pain surrounding procedural sedation is not limited to the procedure itself, but the elapsed time from the time the patient enters the ED to the time spent in preparation for the procedure can be significant and lead to increased anxiety. This may lead to increased time and difficulty in sedating a patient to an appropriate level for a procedure. These patients may require higher levels of propofol to appropriately sedate, which is associated with increased rates of adverse respiratory events.

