We believe that pre procedure adjunctive nitrous oxide may provide a level of anxiolysis and analgesia before propofol is administered, leading to a smoother and more satisfactory sedation and procedure, with fewer adverse respiratory events and less overall propofol dose than propofol alone. Since this is a novel concept, we believe that a pilot study to evaluate the safety and efficacy of pre-procedure adjunctive 50/50 nitrous oxide administration with adult propofol administration is warranted.

Setting of the Research

Patients will be recruited from the Emergency Department of Einstein Medical Center Philadelphia. The Einstein Medical Center Philadelphia is an urban teaching hospital, level one trauma center with 500 beds and an annual ED census of 100,000 subjects.

Resources Available to Conduct this Research

The Einstein Medical Center Philadelphia ED sees approximately 300 patients a day, of which 5% are emergencies that require procedural sedation and analgesia, and thus will be available as potential subjects in this study. The Division of Clinical Research of the Department

of Emergency Medicine has extensive experience in both investigator led and pharmaceutical research. This will be the seventh trial we have conducted in our ED in procedural sedation and analgesia in the last 7 years, and each of these studies has recruited 100-200 patients. We have a research associate 7 days a week who will consent and enroll eligible patients. The division also has 2 full time coordinators and a full time division director, as well as biostatistician support. We have two well-equipped offices, one in the ED where the research associate is based and one in our department where our division director works. The lead investigator will lead 10% of their non-clinical time to this endeavor.

Study Design

This pilot study will be conducted in a prospective, non-randomized fashion using a convenience sample of 100 subjects undergoing sedation for ED procedures.

1. Recruitment Methods

The research associates as well as the health care team (both residents and attending physicians) will screen patients who may need procedural sedation in the ED and may qualify for the study. Research associates will use the Cerner/AeCIS System for screening, and they will be in charge of informed consent, enrollment, placement of the capnography monitor, as well as data collection. The health care team will be in charge of the procedural sedation and all other management.

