2. Inclusion and Exclusion Criteria

- i. Inclusion criteria: All spontaneously breathing subjects, 18 years of age and older, with an American Society of Anesthesiologists (ASA) Physical Status Classification 1 or 2, who will be receiving sedation for an ED procedure.

Written informed consent will be obtained from all subjects.

- ii. Exclusion criteria: Subjects with underlying conditions that could affect ventilation, perfusion, or metabolism including intubated subjects, subjects with clinical signs of cardiopulmonary instability, major trauma, shock, sepsis, ASA class 3, 4, and 5. Also those unable to provide informed consent, nursing home residents, age less than 18 years, non English speaking, pregnant women, subjects under police custody, or physician discretion.

3. Study Endpoints

- i. Primary:

1. ETCO₂ measured q 20 milliseconds seconds
2. SpO₂ measured q 20 milliseconds seconds

- ii. Secondary Endpoints

1. A baseline reading of the vital signs (heart rate, respiratory rate, peripheral SaO₂ and ETCO₂)
2. Physician interventions (verbal or physical stimulation, airway repositioning, additional oxygen, positive pressure ventilation, endotracheal intubation)
3. Level of sedation (Ramsay Score)
4. Patient Demographics
5. Patient recall of procedure
6. Total propofol dose
7. Total elapsed time of nitrous oxide use
8. Patient and physician procedure satisfaction score

4. Procedures Involved in the Research

Initial medical assessment will be made in accordance with established clinical procedures, including the history, physical examination, and vital signs. If by clinical assessment the patient meets eligibility criteria, then they will be approached by a research associate for enrollment in the study. After informed consent is obtained and prior to starting the sedation, standard vital sign monitoring will be placed on the patient (electrocardiogram, non-invasive blood pressure monitoring, pulse oximetry, and capnography). Level of consciousness will be determined using the modified Ramsay scale, which will be assessed at baseline. The Capnostream 20 ETCO₂ monitor will be used as the primary device to measure ETCO₂, with a nasal cannula capable of delivering supplemental oxygen and measuring ETCO₂ (Oridion Medical, Needham, MA).

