The SEDARA gas mixer system [Linde Gas North America LLC] will be used as our primary nitrous oxide delivery device. It will mix and deliver nitrous oxide and oxygen in a 1:1 ratio, at a fixed concentration of 50%/50%. It uses a patient driven demand valve system that is hand held. This device provides a consistent, fixed 50%/50% blend of nitrous oxide (N₂O) and oxygen (O₂), eliminates the need to titrate, and provides fixed concentrations for controlled and consistent dosing. The device comparator detects dosing imbalance to protect against hypoxic mixtures, it cannot deliver nitrous gas without concurrent oxygen, and the device has an anti-asphyxia valve override. The on demand valve requires patient inspiration to trigger dosing. This portable device scavenges exhaled waste gases for environmental safety, as well as a key mechanism that renders the system inoperable without it for security.

After informed consent, the patient will fill out a pre procedure questionnaire and a 100 mm VAS baseline pain scale. The patient will be given the mask for delivery of nitrous oxide, and instructed on its use. The research associate will mark the time the patient began using the device electronically on the capnostream 20. Once IV access is established, and the team and

patient are ready to begin the procedure, the nitrous oxide mask will be removed, and a 100% NRB mask delivering 15 liters a minute of supplemental oxygen will be placed on the patients face. The loading dose of propofol will then be administered immediately. All sedations in this trial will use propofol 1.0 mg/Kg initial dose, with 0.5 mg/Kg doses titrated to deep sedation. Once the patient is deeply sedated, the procedure will begin.

The subject's clinical data and sedation information (refer to data management) will be entered into a standardized data collection form. The data will be continuously recorded throughout the sedation and recovery periods. Study will end when the subjects recovers back to baseline mental status.

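### The Objective claims efficacy for analgesia and pre-procedure anxiolysis, but the protocol body schedules no pain or anxiety score between the start of nitrous oxide and propofol, and lists neither as an endpoint

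*Combined protocol and SAP*

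**What the plan says.** The Objectives section reads: "To describe the safety and efficacy of adjunctive nitrous oxide pre-propofol administration for analgesia and pre-procedure anxiolysis". The Significance section says that nitrous oxide with propofol "may be an ideal agent to decrease pre-procedure anxiety before deep sedation of adults in the ED", and that given before the procedure it "may provide a level of anxiolysis and analgesia before propofol is administered". The intended effect thus belongs to the interval between starting nitrous oxide and loading propofol.

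On measurement, section 4 (Procedures Involved in the Research) states that after consent "the patient will fill out a pre procedure questionnaire and a 100 mm VAS baseline pain scale". The patient then receives the mask. When patient and team are ready, the mask is exchanged for an oxygen mask and propofol is loaded at once. A second 100 mm VAS, with no construct named, is completed after the return to baseline mental status, together with a satisfaction questionnaire and a recall question.

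Specific Aims states: "Secondary aims include patient, nursing, and physician post procedure satisfaction scores, Ramsay sedation scores, total propofol dose given", and goes on to nitrous oxide time and recall. Section 3 (Study Endpoints) has two primary endpoints, ETCO₂ and SpO₂, and eight secondary ones, ending with "Patient and physician procedure satisfaction score". Statistical Methods gives a general descriptive summary of clinical observations and no analysis specific to the VAS.

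**The concern.** A descriptive pilot needs no power calculation or control arm to meet an objective like this one, but it must observe the thing it sets out to describe. Here the stated effect has a short, defined window, and the body places no pain or anxiety reading inside it.

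The outcomes that are collected lie downstream. Satisfaction, recall and the second VAS follow propofol (which the protocol itself calls amnestic), the procedure and recovery. Propofol dose and physician interventions have no comparison group. None of them shows directly whether pain or anxiety fell while nitrous oxide was acting. A reading not taken in that window cannot be reconstructed after enrolment.

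**Working it through.** The documents give no figure to reproduce for this point: there is no power calculation, and the planned 100 subjects are not tied to pain or anxiety. The check sets the order of events against the measurements, then counts labels.

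**Order of events (section 4, Procedures)**

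1. Consent.
2. Pre-procedure questionnaire and baseline pain VAS: first VAS reading.
3. Mask given; the start of nitrous oxide is marked on the monitor.
4. Nitrous oxide in use. Significance says "our patients will be receiving 50/50 nitrous oxide for 5-10 minutes maximum"; Procedures sets no limit of its own.
5. Mask exchange, then the propofol load immediately.
6. Deep sedation and procedure.
7. Return to baseline mental status; satisfaction questionnaire, VAS of unnamed construct, recall: second VAS reading.

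VAS readings scheduled: 1 + 1 = 2. Pain or anxiety scores specified from step 3 to the propofol load in step 5: 0.

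**Items labelled pain or anxiety**

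- Secondary aims: three satisfaction scores, Ramsay, propofol dose, nitrous oxide time, recall = 7; labelled, 0.
- Study Endpoints: 2 primary + 8 secondary = 10; labelled, 0.
- Data Management list: age, gender, weight (3); BP, HR, RR, SpO₂, ETCO₂ (5); nitrous oxide time, start time, return-to-baseline time, elapsed sedation time, medications, repeat doses and times, total doses, adverse events, interventions (9); Ramsay (1). 3 + 5 + 9 + 1 = 18; labelled, 0.
- Time-stamped events: propofol administration, procedure start, procedure completion, adverse events, physician interventions = 5; labelled, 0.

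The first step (no score in the window) and the endpoint count carry the argument. The last two lists are weaker evidence: Data Management also omits satisfaction, recall and the baseline VAS, all of which are collected, and the time stamps are monitor events.

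**Could the Ramsay score fill the gap?** Study Endpoints lists it as level of sedation. Procedures puts it at baseline and at deepest sedation; Data Management puts it at baseline and at undefined intervals during sedation. A reading during nitrous oxide use is neither specified nor clearly excluded. Significance describes nitrous oxide as having minimal sedative effect, so a sedation score would be a poor stand-in for analgesia or anxiolysis.

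**Context only: precision of one added reading.** The documents give no SD for VAS change. Assuming 20 to 30 mm and 100 complete pairs, the 95% CI half-width for mean change is t(0.975, 99) × SD / √100:

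- SD 20 mm: 1.984 × 20 / 10 = 3.97 mm.
- SD 30 mm: 1.984 × 30 / 10 = 5.95 mm.

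This shows what a single reading could deliver. It does not measure the size of the problem.

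**The case against.** The strongest objection is that the forms are not visible. The pre-procedure questionnaire, the post-procedure questionnaires, the data collection form, the Ramsay scale and the satisfaction instrument are not reproduced, and item-level content and timing may sit there. That stands as a limit, and the conclusion is confined to the protocol body. The pre-procedure questionnaire, as sequenced, comes before the mask and could supply only a baseline. If another form does hold a reading in the window, its timing and endpoint status still belong in the body.

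A second objection is that efficacy was deliberately defined downstream. The investigators expect early anxiolysis and analgesia to lead to a smoother, more satisfactory sedation with less propofol, and the secondary aims match that. The analgesia and anxiolysis wording could also be read as the purpose of giving the gas, not as a promise to measure it. This is a fair reading and is why narrowing the Objective is an acceptable remedy. It does not rescue the current wording, because the downstream outcomes have no comparator and cannot describe an effect before propofol.

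Third, an added change score in a single group would still mix time, expectation and co-medication. That is true, and it should be reported as descriptive. It would still be a direct observation, which the body now lacks. The general summary in Statistical Methods may cover the two scheduled VAS readings, but it cannot supply one that was never scheduled.

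**Conclusion.** The concern holds for the protocol body. Two VAS readings are scheduled, none of them between nitrous oxide start and propofol. No anxiety scale is named, and 0 of 10 endpoints is labelled pain or anxiety. If the body is followed exactly and the unseen forms add nothing, pre-propofol pain and anxiety are not directly observed, and the efficacy part of the Objective rests on indirect outcomes. The post-procedure VAS, probably pain, cannot isolate nitrous oxide analgesia because it reflects the whole sedation and the completed procedure.

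The primary safety aim and the planned sample size are not affected. This should be corrected but does not undermine the study. Confidence is medium because the forms could not be examined.

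**What to change.** Unless the forms already provide for it:

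- Record a 100 mm anxiety VAS alongside the baseline pain VAS.
- Have the research associate repeat both while nitrous oxide is in use, just before mask removal. The reading must not change the timing of the sedation; if it is not obtained, record it as missing.
- List both as secondary endpoints. Report paired change (pre-mask-removal minus baseline) with a 95% CI, the number evaluable and the number missing, labelled descriptive because there is no control arm.
- Name the construct of the post-procedure VAS and interpret it as reflecting the whole sedation.

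If the forms already hold these readings, state their timing in the protocol body and list them as endpoints. If the reading is not to be added, narrow the Objective to the outcomes actually collected.

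The cost is one brief extra form. No new staff are needed: under Recruitment Methods, of the research associates, "they will be in charge of informed consent, enrollment, placement of the capnography monitor, as well as data collection". The drawbacks are an added step while the patient is holding a demand device and the team is ready to begin, some missing readings, and a change score that remains uncontrolled. Narrowing the Objective is only a wording change, but it gives up the direct efficacy question.

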Vital signs will be flagged electronically when a physician intervenes for clinical respiratory depression. Respiratory depression will be defined as peripheral SaO₂ below 92%, ETCO₂ level above 50, a rise or decrease of 10% above or below baseline, the loss of the ETCO₂ waveform for more than 15 seconds. Level of consciousness will be determined using the modified Ramsay scale, which will be recorded at baseline and at the point of deepest sedation. Once the procedure is complete, and the patient is deemed back to their mental status baseline, they will fill out a post procedure satisfaction questionnaire, and a 100mm VAS scale. They will be asked about procedure recall. The physician will also fill out a post procedure questionnaire.

5. Data Management

A standardized data collection form will be used to collect clinical data and a USB drive to collect electronic vital sign data. Initial data gathered will include age, gender, weight, and baseline vital signs (BP, HR, RR, peripheral SpO₂, and ETCO₂). Other information collected will be the elapsed time of nitrous oxide use, start time (when protocol was given), time (when patient returns to baseline), elapsed time in seconds under sedation (from start time to end time),

medications administered, repeated doses and times for every administered medication, total dose of each medication administered, adverse events, and interventions aimed at correcting respiratory depression. Level of consciousness using the modified Ramsay scale will also be recorded at baseline and at set intervals during sedation.

The electronic monitoring data will be continuously recorded into the USB drive throughout the sedation and recovery periods. The Capnostream 20 ETCO₂ monitor (Oridian Medical, Needham, MA) is capable of sampling and recording ETCO₂ and pulse SaO₂ every 5 seconds. A patient identifier will be recorded to link the subject and the electronic monitoring data without compromising his/her confidentiality. At the completion of the sedation, all device data will be transmitted to a password-protected Excel/SPSS spreadsheet for analysis. The research associate is responsible for recollection and storage of the data. Only the primary investigators, the study coordinator, and the research associates will have access to such.

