To assess these outcomes, we will download electronic data from each sedation into a Microsoft Excel database, checked and adjudicated any discrepancies with research associate notations, and generate a graph of the subject's sedation with the X-axis showing time and the Y-axis depicting ETCO₂, SpO₂, respiratory rate, and heart rate. Electronic time stamps noted propofol administration, procedure initiation and completion, adverse events, and physician interventions.

Before study blinding is broken, three investigators will evaluate each graph to code the presence or absence of cerebral hypoxia, peripheral hypoxia and respiratory depression. We will disqualify graphs if they had >35% data loss, unless all three evaluators agreed that there was unequivocal evidence of hypoxia (cerebral and or peripheral) and/or respiratory depression.

6. Withdrawal of Subjects

Participation is voluntary. Subjects may withdraw from this study at any time. If this is the case their data will be deleted. We will record the number of patients that withdraw. Subjects may be withdrawn without their consent if the electronic data cannot be recorded.

Statistical Plan

1. Sample Size Determination

As this is a pilot, prospective, observational trial, no power calculation will be used to measure a difference. In previous propofol studies, approximately 10-30% of patients develop hypoxia, and approximately 50% of patients meet criteria for respiratory depression. Thus, we believe enrolling 100 patients in this observational trial will allow for approximation of any correlations that are measured.

2. Statistical Methods

All clinical observations and demographic data will be summarized using medians with range or means with standard deviations as appropriate. Rate of detection of respiratory depression and hypoxia and timing of these events for each instrument (near-infrared spectroscopy, pulse oximetry, capnography) will be summarized descriptively. Associations among SaO₂, and ETCO₂ will be estimated using spearman's rank correlation coefficient, using within-cluster resampling algorithm. This will allow for estimation of the marginal correlation in the presence of clustered data. Correlations not involving repeated measures data will be estimated with Spearman's rank correlation coefficient. All analysis will be conducted using SPSS software (IBM, Armonk, NY).

Risks to Subjects

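### The coded respiratory event rests on monitor limits alone, so a subject treated on clinical judgement before a limit is crossed meets no event definition, and no planned analysis links crossings to interventions

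*Combined protocol and SAP*

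**What the plan says.** The Specific Aims give the target: "To measure the rates of hypoxia and respiratory depression requiring a physician intervention".

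Study Design, section 4 (Procedures Involved in the Research) then uses two notions of the event in adjacent sentences. The first is bedside judgement: "Vital signs will be flagged electronically when a physician intervenes for clinical respiratory depression". The second is numerical: "Respiratory depression will be defined as peripheral SaO₂ below 92%, ETCO₂ level above 50, a rise or decrease of 10% above or below baseline", with loss of the ETCO₂ waveform for more than 15 seconds as the last criterion. Intervention is not among the criteria.

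On who acts, section 1 (Recruitment Methods) says "The health care team will be in charge of the procedural sedation and all other management". On what that team can see, section 4 says "standard vital sign monitoring will be placed on the patient (electrocardiogram, non-invasive blood pressure monitoring, pulse oximetry, and capnography". The plan does not say that the display is hidden from the team, and no rule ties an intervention to a limit.

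Interventions are recorded in several places. Section 3 (Study Endpoints) lists "Physician interventions (verbal or physical stimulation, airway repositioning, additional oxygen, positive pressure ventilation, endotracheal intubation" as a secondary endpoint. Section 5 (Data Management) collects "interventions aimed at correcting respiratory depression" on the form and describes electronic time stamps for interventions.

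For coding, section 5 says "three investigators will evaluate each graph to code the presence or absence of cerebral hypoxia, peripheral hypoxia and respiratory depression". Statistical Plan, section 2 (Statistical Methods) summarises the rate and timing of these events descriptively, by instrument. It does not mention interventions.

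**The concern.** The listed interventions act on the signals that define the event. Stimulation that restores breathing 10 seconds into a lost waveform means the 15-second criterion is never met. Extra oxygen while saturation is falling can keep the reading from going below 92%. In either case a physician judged breathing to be depressed and treated it, yet the graph may show no crossing.

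The aim makes the need for intervention part of the event, while the coding rule leaves intervention out. Safety is the stated objective and there is no control arm. The Significance section expresses a belief in fewer adverse respiratory events than with propofol alone. Readers will therefore be inclined to set the observed rates against the 10-30% hypoxia and roughly 50% respiratory depression quoted under Sample Size Determination. If a material number of subjects were treated without a crossing, the threshold rate alone would not show it.

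**Working it through.** 1. **The plan's own figure.** The sample size of 100 comes with no alpha, power, effect size or target precision, so there is no calculation to reproduce.

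2. **Classification.** A subject either crosses a limit or does not, and either has a flagged intervention or does not. Under the section 4 definition, both crossing cells are coded present and both non-crossing cells absent. The cell with an intervention but no crossing has no rule of its own, so the definition places it under absent.

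3. **Two separate rates do not recover the joint result.** If a of 100 subjects cross and b have an intervention, the number with both lies between max(0, a + b − 100) and min(a, b). For illustration, take a = 50 (the plan's 50%) and assume b = 20. The number with both can be anything from 0 to 20, so the number treated without a crossing can be anything from 20 to 0. The aim concerns this joint result, and the planned summaries do not fix it.

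4. **Sampling error at n = 100.** Half-width = 1.96 × √(p(1 − p)/100), which gives 5.9 points at 10%, 9.0 at 30% and 9.8 at 50%. The exact 95% intervals are 4.9-17.6%, 21.2-40.0% and 39.8-60.2%.

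5. **Sensitivity to early action.** Let p be the rate if nobody acted before a crossing, and f the share of would-be crossings averted. If early action only removes crossings, the coded rate is p(1 − f). The documents give p (10%, 30%, 50%). They do not give f, so 10% to 50% is assumed.

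| p | f = 10% | f = 20% | f = 30% | f = 50% |
|---|---|---|---|---|
| 10% hypoxia | 9% | 8% | 7% | 5% |
| 30% hypoxia | 27% | 24% | 21% | 15% |
| 50% respiratory depression | 45% | 40% | 35% | 25% |

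The exact interval around the coded rate is then compared with p:

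- p = 30%: at f = 30% the interval is 13.5-30.3% and still contains 30%. At f = 50% it is 8.6-23.5% and does not.
- p = 50%: at f = 20% the interval is 30.3-50.3% and still contains 50%. At f = 30% it is 25.7-45.2% and does not.
- p = 10%: the interval contains 10% at every f tried. At f = 50% it is 1.6-11.3%.

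6. **What a composite would show.** Let g be the assumed share of all subjects with an intervention but no crossing. The composite is the threshold rate plus g:

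| Threshold rate | g = 5% | g = 10% |
|---|---|---|
| 10% | 15% (8.6-23.5%) | 20% (12.7-29.2%) |
| 30% | 35% (25.7-45.2%) | 40% (30.3-50.3%) |
| 50% | 55% (44.7-65.0%) | 60% (49.7-69.7%) |

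If every averted crossing followed a flagged intervention, the composite is an upper bound on the rate without early action, because some of those treated would not have gone on to cross.

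**The case against.** A reader might infer something stronger: that early rescue erases the event, that the coded rates are biased downward, and that quick physicians would pass for a benefit of nitrous oxide. The documents do not support this, for five reasons.

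- **Nothing is erased.** Interventions are flagged, time-stamped, collected on the form and named as a secondary endpoint. A subject treated without a crossing can be found in the data.
- **Bias needs a target the plan does not adopt.** The objective is to describe safety during ED sedation, with the treating team in charge. For that purpose the rate under ordinary physician response is a legitimate target. A rate without rescue is a hypothetical that the plan nowhere requests.
- **No comparison is planned.** The 10-30% and 50% stand in a paragraph that disclaims any power calculation for a difference. Rescue practice in those earlier propofol studies is not described, so earlier action here than there cannot be shown.
- **Direction is less clear for respiratory depression.** A 10% change in either direction is a sensitive criterion. If it refers to ETCO₂, an assumed baseline of 40 would be crossed at 36 or 44, perhaps before anyone acts. Stimulation or ventilation might also disturb the ETCO₂ trace and create a crossing. The p(1 − f) formula ignores this.
- **Coding as absent is implied, not stated.** Section 5 describes intervention time stamps close to the graph reading and provides for adjudication against research associate notes, so graders may take interventions into account.

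All five points stand against the stronger reading. None supplies the missing rule for an intervention without a crossing, or the missing link between two separately reported rates. Graders who may or may not count interventions are a further reason to write the rule down.

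There is also a fair case against making a composite the main rate. It would count crossings with no intervention, which the aim does not name. It would also no longer match the quoted 50%, which refers to patients meeting criteria.

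**Conclusion.** The point holds as a mismatch between aim, definition and analysis. As defined, the coded rates are rates under ordinary physician response. They may understate respiratory compromise, because a subject treated on clinical judgement before a limit is reached meets no coded definition. The loss is more plausible for saturation below 92% than for respiratory depression as a whole, given the sensitive 10% criterion; this is reasoning, not a documented figure.

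The size is unknown. Under the removal-only assumption, at n = 100, the shift stands clear of sampling error only when the averted share is large: 50% for a 30% hypoxia rate, 30% or more for a 50% respiratory depression rate, and at no tested value for a 10% hypoxia rate. Bias against the quoted background rates is possible but not shown. The case for a change is that the data are already to be collected and the joint result named in the aim cannot be read from the summaries as planned.

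**What to change.** Add to the coding rule in Data Management, with a matching line in Statistical Methods:

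- From the existing flags and time stamps, place each subject in one of four classes: crossing then intervention; crossing without intervention; intervention for respiratory depression before or without a crossing; neither. Order subjects by their first crossing and first flagged intervention, and within the third class show how many later crossed.
- Report this table, with time order, beside the threshold-defined rate. Keep the threshold rate as the main rate, since its definition is closest to that of the quoted figures.
- Give the composite of crossing or intervention, with its confidence interval, as a sensitivity rate labelled as an upper bound.
- Tell graders how to code a graph that has an intervention but no crossing.
- State that the coded rate is the rate under usual physician response.

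The cost is some plan wording and a short program on recorded time stamps. No new data and no change to patient care are needed. The small downside is a little more analysis and an intervention class that partly reflects physician judgement; showing the classes separately keeps that visible.
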